## **6 Study Enrollment and Withdrawal**

Eligible participants will be recruited from the Emergency Department at Bellevue Hospital and NYU Langone Health sites, including NYULH-Tisch, NYULH-Brooklyn, NYULH-Cobble Hill. The Bellevue Hospital ED has an annual patient volume of approximately 120,000 visits, which includes a large volume of patients with moderate or severe OUD who will be eligible for study participation. All patients who come to the Bellevue Hospital ED in opioid withdrawal may be screened by eligibility criteria for potential study enrollment (see Inclusion and Exclusion criteria, defined below). Patients may be referred to the study team by ED clinicians at NYULH sites listed above. Eligibility requirements will be determined by trained research staff in the ED and will be confirmed by the PI or co-investigator if there is any question of potential eligibility.

### **6.1 Inclusion Criteria**

In order to be eligible to participate in this study, an individual must meet all of the following criteria:

Study Number: s19-01700

Version: 7.0

Version Date: 08/01/2022

1. Is 18 years or older
2. Is able to speak English sufficiently to understand the study procedures and provide written informed consent to participate in the study. The study instruments have not been validated in Spanish (or other languages). Given the small size of this pilot, it would not be feasible to translate and validate them.
3. Meets DSM-5 criteria for moderate to severe OUD
4. Has used opioids within 7 days, confirmed by a positive toxicology test and/or by the clinical assessment by the study clinician or ED provider (e.g., self-report plus documented history of opioid use and objective findings consistent with opioid withdrawal).
5. Denies use of methadone at a dose that is greater than 30mg within 72 hours or greater than 10mg within 24 hours or at an unknown dose
6. Must be experiencing opioid withdrawal with a COWS score  $\geq 8$ .
  - a. Enrollment and assessments (but not study medication administration) may begin at COWS <8 if patient is anticipated to have a COWS score  $\geq 8$  during their ED visit.
7. Is willing and able to participate in the study and follow study procedures, including completing a 90-minute minimum observation period in the ED after their second dose of BUP, in-person assessments on days 1-3, and a phone assessment on day 30.
8. Is able to provide adequate and reliable locator information for follow-up
9. Has reliable access to a phone

## 6.2 Exclusion Criteria

An individual who meets any of the following criteria will be excluded from participation in this study:

1. Is currently engaged in medication treatment for OUD with methadone, BUP, or naltrexone
2. Currently requires prescribed opioids for treatment of an ongoing pain condition
3. Has a known allergy to BUP
4. Is pregnant as determined by hCG testing at the index ED visit
5. Is breastfeeding as determined by self-report
6. Has medical, psychiatric, or concurrent substance use conditions or severe cognitive impairment that might preclude safe participation in the study as determined by the study clinician or the clinical provider, or such that they are unable understand the study procedures and provide written informed consent to participate in the study
7. Is a prisoner or in police custody at the time of the index ED visit
8. Has previously enrolled in the current study

## 6.3 Vulnerable Participants and Individuals

Eligibility requirements will be determined by trained research staff in the ED, and will be confirmed by the PI or co-investigator if there is any question of potential eligibility. This study will not include children, pregnant women, prisoners, or individuals with impaired decision-making capacity. By nature of the population served by the Bellevue Hospital ED and NYULH EDs, participants may include economically or educationally disadvantaged persons, but every effort will be made to consent these patients appropriately. Patients may also fear that they will not receive adequate treatment for OUD, overdose or withdrawal if they do not consent to participate in this study. It will be made explicit that their choice to participate or not will not affect their treatment. If there is any question that the nature of a subject's vulnerability has influence over participation in the study, the subject in question will be excluded.

## 6.4 Strategies for Recruitment and Retention

As described previously, potential participants will be identified and screened after presenting to the Bellevue Hospital ED in opioid withdrawal. Using methods employed successfully in our previous and ongoing studies, potential participants will be identified by clinician referral or clinical screening. Patients may be referred to the study team by ED clinicians at NYULH-Tisch, NYULH-Brooklyn, NYULH-Winthrop, and NYULH-Cobble Hill.

The research team will be notified of potential participants and determine whether they meet eligibility criteria. Subjects will be approached by trained research staff who will request the patient's verbal consent to inform them about the study and determine whether they are interested using an IRB-approved verbal consent script. Written informed consent will be obtained before any study activities are performed. After they are consented, we will perform additional assessments to confirm eligibility followed by pre-treatment

Study Number: s19-01700

Version: 7.0

Version Date: 08/01/2022

assessments as detailed in Section 6.9.4: *Dosing and Administration*. Individuals who meet any exclusion criteria will not be enrolled or will be withdrawn from the study if already enrolled as post-enrollment screen fails.

Efforts will be made to maintain contact with patient-participants throughout the duration of the study and to minimize missing data. Broadly, retention methods may include outreach to the participant and their identified contacts through email reminders, phone calls, text messaging, and social media.

A total of 35 participants will be enrolled in the study with the goal of having 30 participants complete the study in its entirety.

#### **6.4.1 Use of DataCore/Epic Information for Recruitment Purposes**

Patients will be recruited in-person by the research team during their ED visit without the use mail, email, or other messaging to patients or the use of patient-facing recruitment materials. Identification of potential participants will occur primarily through referral by clinical staff (health coaches, social workers, peer counselors, and volunteers) who operate an existing substance use screening and intervention program in the Bellevue ED. EPIC will be utilized in a limited capacity to identify participants. Specifically, the research team will review the census of current, active ED patients in EPIC to identify patients who have ED visits related to opioid use and/or who have been identified to have non-medical opioid use (e.g., nurse screening) and/or who have been identified and referred by clinical staff as potential study participants. The research team will inform the treating provider that their patient is potentially eligible for the study and will request permission to be introduced to the patient. The research team will use approved recruitment language to communicate the reason they are approaching the patient and ask if they are interested in participating in this specific study. Should the potential participants agree, the research team will provide the subjects with information regarding the next steps for participation.

If a subject requests information regarding opting out of further recruitment for all research, subjects will be directed to contact [contact] or [name].

#### **6.5 Duration of Study Participation**

The study duration will be approximately 12 months. The duration of study participation for each individual participant will be 1 month, including screening/index visit, study intervention and follow-up. We will target 1 study enrollee per week, with a goal of 2 per week, and expect to enroll participants within an 11-month period. The study will end approximately one month after the final participant is enrolled, at the conclusion of that participant's one-month follow up. We know from our previous and ongoing studies that recruitment should not be limited by the number of eligible patients.

#### **6.6 Total Number of Participants and Sites**

Recruitment will end when approximately 35 participants are enrolled. Enrollment will take place out of the Emergency Departments in Bellevue Hospital, NYULH-Tisch, NYULH-Winthrop, NYULH-Brooklyn, and NYULH-Cobble Hill.

#### **6.7 Participant Withdrawal or Termination**

##### **6.7.1 Reasons for Withdrawal or Termination**

Participants are free to withdraw from participation in the study at any time upon request. An investigator may terminate participation in the study if:

- After the first 8 mg dose of BUP is administered, a study participant experiences any clinical AE (e.g., allergic reaction) that would preclude safe administration of the subsequent BUP 24mg dose during the index visit. The initial BUP 8mg is a standard dose used in the ED; it is only the subsequent BUP 24mg (for a total dose of BUP 32mg) that is being evaluated in this study.
- Thus, if a participant develops a reaction to the initial 8mg dose, the reaction would be attributed to the standard dose of BUP and not the larger dose of being tested.
- The participant meets an exclusion criterion (either newly developed or not previously

Study Number: s19-01700

Version: 7.0

Version Date: 08/01/2022

recognized) that precludes further study participation.

- The participant becomes a prisoner.

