Study Sites	The study will take place in the Emergency Departments at Bellevue Hospital and NYU Langone Health sites including NYULH-Tisch, NYULH-Brooklyn, NYULH-Winthrop, and NYULH-Cobble Hill.
Number of participants	35 participants
Description of Study Agent/Procedure	BUP 32 mg SL (in two doses of 8mg and 24mg)
Key Procedures	Urine or saliva test, administration of BUP 32 mg SL.
Statistical Analysis	Statistical analyses will consist of descriptive analyses and will provide summary tabulations and measures of central tendency, variance, and other distributional properties of the obtained results. Where applicable, we will also conduct cross-tabulations and comparative analyses of variance based on selected key characteristics of the study participants (e.g., sex, age categories, withdrawal scores at baseline).

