### **6.9.4 Dosing and Administration**

All participants will receive a total dose of BUP 32mg sublingually in divided doses during the index ED visit. After the participant has received a total of 8mg (as a single dose or in divided doses), BUP SL 24mg will be administered (i.e., 8mg + 24mg, or 4mg + 4mg +24mg). A dose of up to BUP 8mg SL may be administered by the clinical provider prior to enrollment of the patient-participant (i.e., given clinically, not as a research procedure).

After pre-medication assessments are complete and the participant is confirmed to have a COWS of  $\geq 8$ , the participant will be given BUP SL to reach a dose of 8mg. Starting 30 minutes after BUP administration, the participant will be reassessed for withdrawal severity and any adverse events. As long as there are no unexpected significant adverse events, an additional BUP 24mg SL will be administered. Then, participants will be monitored and reassessed every 30 minutes for a period of at least 90 minutes after receiving the last dose of BUP.

Participants will return on days 1, 2, and 3 for research visits. At those visits, participants will be assessed for opioid withdrawal using the COWS scale. On the first day that the participant has objective signs of opioid withdrawal (via COWS), the [name], who is a licensed physician with an X-waiver for BUP prescription, or another study clinician (with the appropriate license and X-waiver) will electronically send a prescription the participant's preferred outpatient pharmacy for a daily dose of BUP 16mg (BUP or BUP/NX 8/2mg: two SL) to start immediately. Participants will be prescribed a quantity sufficient to ensure medication coverage until the date of their appointment for ongoing treatment with a (non-study) OUD treatment provider. Participants who do not exhibit opioid withdrawal at any of the visits on days 1-3, will be given a prescription upon completion of the day 3 visit with instructions to self-administer upon emergence of symptoms of opioid withdrawal or craving.

All participants will receive a referral to be seen by a provider experienced in treating OUD. Thereafter, continued treatment and specific daily dosage of BUP-NX will be a joint decision between the study participant and the healthcare provider.

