### **6.9.10 Study Agent Accountability Procedures**

See Section 6.9.6. The initial 32mg loading dose of BUP will be dispensed from the Bellevue Hospital ED medication dispensing system and administered by a member of the research team in conjunction with the treating clinician. Participants will be given a prescription for BUP-NX (16mg daily in 8mg tablets/films) to last between their third research visit and their appointment for continuing treatment.

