## **8.2 Classification of an Adverse Event**

### **8.2.1 Severity of Event**

AEs are graded according to the following scale:

**Mild:** An experience that is transient, and requires no special treatment or intervention. The experience does not generally interfere with usual daily activities. This includes transient laboratory test alterations.

**Moderate:** An experience that is alleviated with simple therapeutic treatments. The experience impacts usual daily activities. Includes laboratory test alterations indicating injury, but without long-term risk.

**Severe:** An experience that requires therapeutic intervention and/or interrupts usual daily activities. If hospitalization (or prolongation of hospitalization) is required for treatment it becomes an SAE.

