### **8.2.2 Relationship to Study Agent**

The study uses the following AE attribution scale:

Study Number: s19-01700

Version: 7.0

Version Date: 08/01/2022

**Not related:** The AE is clearly not related to the study procedures (i.e., another cause of the event is most plausible and/or a clinically plausible temporal sequence is inconsistent with the onset of the event).

**Possibly related:** An event that follows a reasonable temporal sequence from the initiation of study procedures, but that could readily have been produced by a number of other factors.

**Related:** The AE is clearly related to the study procedures.

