## **8.6 Study Halting Rules**

Administration of study agent will be halted when three grade 3 AEs determined to be "probably related" are reported to the sponsor. When the third grade 3 event is reported, enrollment screens will stop accepting new study participants. The study sponsor will inform the DSMB members within 24 hours of this occurrence and will provide the DSMB with AE listing reports. The DSMB will convene an ad hoc meeting by teleconference or in writing as soon as possible. The DSMB will provide recommendations for proceeding with the study to the study sponsor.

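### The section 8.6 halting rule counts adverse events at a relatedness level that section 8.2.2 does not contain, and section 6.7.1 leaves unclear whether reactions to a study-given first 8 mg count toward it

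*Combined protocol and SAP*

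**What the plan says.** **The halting rule and the scales.** Under section 8.6, administration of study agent "will be halted when three grade 3 AEs determined to be" *probably related* are reported to the sponsor. Screening for new participants then stops and the DSMB holds an ad hoc review. Section 8.2.1 states that "AEs are graded according to the following scale" and lists mild, moderate and severe. Section 8.2.2 lists not related, possibly related and related. Its top level reads "The AE is clearly related to the study procedures", so the reference is study procedures, and no exception is made for the first dose.

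**The first 8 mg.** Section 6.7.1 calls the initial 8 mg a standard ED dose and says that only the following 24 mg is under evaluation. Of a reaction to the initial dose it says that "the reaction would be attributed to the standard dose of BUP and not the larger dose of being tested". Section 6.9.4 distinguishes two routes to the first 8 mg. Up to 8 mg may be given by the clinical provider before enrolment, "given clinically, not as a research procedure". Otherwise, after assessments and a COWS score of at least 8, "the participant will be given BUP SL to reach a dose of 8mg". The Protocol Summary defines the study agent as "BUP 32 mg SL (in two doses of 8mg and 24mg", and section 6.9.10 has the 32 mg loading dose "administered by a member of the research team in conjunction with the treating clinician".

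**The concern.** A halting rule has to be applicable to the data the trial will hold. Here the rater works with one relatedness scale and the rule asks for a level that is not on it. Whoever keeps the count must decide, perhaps after the events are known, which 8.2.2 ratings qualify.

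Section 6.7.1 adds a second uncertainty. It assigns every first-dose reaction to the standard dose in advance, whoever gave that dose, and does not say how this sits with the rating in 8.2.2. A rater could take it to mean that a severe reaction to a study-given 8 mg is not related to the treatment under test, and so not for the 8.6 count.

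At stake is the one stopping trigger based on a number of events, in a study whose first-day dose of 32 mg exceeds the 8 mg that the label recommends for induction (section 2.1.4).

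**Working it through.** The plan states no halting probability, so there is no figure to reproduce. The check is a comparison of text, followed by small counts.

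**Step 1. Match each qualifier in 8.6 to section 8.2.**

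| Qualifier in 8.6 | Levels available | Match |
|---|---|---|
| *Grade 3* | 8.2.1: mild, moderate, severe | Not a listed term; severe is the third of three levels, so the reading is reasonable |
| *Probably related* | 8.2.2: not related, possibly related, related | None; it could mean possibly related, related, or both |

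**Step 2. See what the gap does to a count.** Take a hypothetical set of three severe events, one rated related and two rated possibly related. The threshold is 3.

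- Literal reading (*probably related* only): 0 events, no halt.
- Related only: 1 event, no halt.
- Possibly related only: 2 events, no halt.
- Both positive levels: 1 + 2 = 3 events, halt.

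The same three events give four different counts, and only one reading halts the study.

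**Step 3. Set 6.7.1 beside the dosing sections.** The attribution sentence has no condition on who gave the 8 mg or when. Section 6.9.4 separates clinical from study dosing, and the Protocol Summary and 6.9.10 place a study-given 8 mg inside the study agent. Section 8.2.2 rates relation to study procedures. Nothing in 6.7.1 says that 8.2.2 still governs a study-given first dose. Equally, 6.7.1 does not mention 8.2.2 or 8.6 and does not call such reactions unrelated to study procedures.

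**Step 4. Effect on the count if 6.7.1 were read as an exclusion.** Three severe related events, one of them after a study-given first dose: 3 − 1 = 2, below the threshold.

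**Step 5. Range under assumed rates (illustration only).** Let *p* be the chance that a participant has one qualifying event, with 35 participants. Then P(halt) = 1 − Σ C(35, k) p^k (1 − p)^(35 − k), summed over k = 0, 1, 2. For the last column, assume that half the events follow a study-given first dose and are not counted, so *p* is halved.

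| Assumed p | All events count | First-dose half left out |
|---|---|---|
| 2% | 0.033 | 0.005 |
| 5% | 0.254 | 0.057 |
| 10% | 0.694 | 0.254 |
| 15% | 0.913 | 0.494 |

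Neither the rates nor the half split is in the documents. The table shows only that a threshold of three is sensitive to what is counted.

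**The case against.** The strongest reply has four parts.

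- **6.7.1 is a reasoned statement about dose, not about relatedness.** It explains that 8 mg is ordinary ED treatment, and section 5.1.1 likewise ties its adverse events to the second dose. A rater can follow both sections by ascribing the reaction to the 8 mg and still rating it under 8.2.2. This stands, and it is why the 6.7.1 part is only a possible reading. It does not remove the need to say so, because the sentence also covers an 8 mg dose that the study gives.
- ***Grade 3* is clear enough.** This stands: severe is the natural reading. The unmatched term is *probably related*.
- **Safety handling does not hang on 8.6.** Section 8.3 requires adverse events to be documented regardless of relationship. Section 8.5 sends serious events to the sponsor whether related or not. Section 8.7 sends all adverse events to the DSMB chair, sponsor and IRB, and lets the principal investigator, DSMB or IRB stop the study. This also stands. A reader might infer that first-dose reactions would go unrecorded or that the study could not be stopped; the documents do not support either inference.
- **A looser rule has a cost.** Possibly related covers events with other ready explanations, and severe includes events that need therapeutic intervention. The fix must own this.

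A reader might also infer that section 8.4.1(a) loses events, since it lists possibly, probably or definitely related. It does not: that list takes in both positive levels of 8.2.2.

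**Conclusion.** The point holds for 8.6. As written, the relatedness condition matches no level of 8.2.2, so the rule cannot literally be met, and any working version depends on an unstated choice. This rests on the text alone and needs no event rate.

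For 6.7.1 the conclusion is limited to an ambiguity: reactions to a study-given first 8 mg might be left out of the halting count. It would be too strong to say that the protocol excludes them.

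The size cannot be estimated. A reader might look for a rate in the chart review of 94 ED patients cited in section 2.1.3, which saw no adverse events. Those patients received 24 to 32 mg, so anyone stopped after a first dose may be missing, and the series gives no rate of severe, related first-dose events. What can be said is that the threshold is three, so misclassifying a single event can decide whether the study pauses. The correction should be made, and it is a matter of wording.

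**What to change.** 1. **Section 8.6.** Restate the rule in the protocol's own categories, for example: halt and DSMB review after three severe adverse events rated possibly related or related to study procedures. Alternatively, add and define a *probably related* level in 8.2.2, keep the present threshold, and write severe in place of *grade 3*.
2. **Section 6.7.1.** Add that the attribution sentence concerns the evaluation of the 24 mg dose only, and that reactions to any study-given buprenorphine, including the first 8 mg, are rated under 8.2.2 and count toward 8.6.
3. **Section 8.4.1(a).** Use the 8.2.2 terms here too. This is tidying only.

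The cost is a few sentences in an amendment; no new data are collected. If possibly related events count, the rule will trigger more readily, by an amount the documents do not allow to be estimated. The consequence of a trigger is a pause for DSMB review. If that is judged too sensitive for 35 participants, adding the extra level in 8.2.2 is the better route.

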### **6.7.2 Handling of Participant Withdrawals or Termination**

If participants are terminated from the study or withdraw themselves for any of the above reasons, the situation will be handled accordingly. If participants choose to withdraw themselves, but have no AEs, they will still be eligible to continue treatment for OUD, which may include BUP, and will be treated with the standard of care and connected to follow-up as clinic availability allows. If participants are terminated or removed due to any AE, they will be monitored and treated either in the ED or on an outpatient basis. If a participant meets exclusion criteria (either newly developed or not previously recognized), they will be formally withdrawn from the study, but may be still be eligible to continue BUP treatment outside of the study. If participants are withdrawn or discontinued early, enrollment will continue to meet a goal of 35 participants.

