## **7.4 Study Schedule**

### **7.4.1 Screening**

### **7.4.2 Enrollment/Baseline**

#### **Index ED Visit (Day 0, 4 – 8 hours)**

- Perform baseline assessments:
  - Obtain demographic information, medical/psychiatric history, medication history, substance use history.
  - Obtain informed consent of potential participant verified by signature on written informed consent for screening form.
  - Perform medical examinations needed to determine eligibility based on inclusion/exclusion criteria.
  - Review history and verify inclusion/exclusion criteria.
  - Collect urine or saliva samples for toxicology testing, collect urine for a pregnancy test (in females of childbearing potential, if not performed clinically).
  - Assess and quantitate opioid and other substance use, withdrawal, craving, motivation for treatment, health status questionnaire, health services utilization).
- Participants receive total 32mg BUP in divided doses. After the participant has received a total of 8mg, participants will be observed for 30 minutes to ensure that there are no adverse reactions to BUP-NX. If the participant has a qualifying adverse event after the first dose (e.g., allergic reaction or other clinically significant AEs as described in Section 5.1.1), the second dose will not be given and the participant will be withdrawn from the study without receiving subsequent doses. Otherwise, the second dose of 24 mg will be administered.
- Participants will be assessed using opioid withdrawal scales (COWS, SOWS, VAS) prior to BUP administration and every 30 minutes afterward for at least 90 minutes after last dose.
- Participants will be discharged with 4 scheduled appointments, 3 research visits (days 1, 2, 3), an appointment for follow up with a BUP provider for ongoing OUD treatment, and a research follow-up phone call on Day 30, which marks the end of the study for the participant.
- In light of the health safety risks associated with the COVID-19 pandemic, interviews may be conducted remotely, rather than in-person, using an approved, secure audio or audio-video connection (e.g., telephone, Cisco Webex) from a setting offering adequate privacy. Participants will be advised that they may disconnect their video feed.

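### Enrolment continues to 35 after any early withdrawal, with no dosing cut-off, and the two primary denominators disagree on whether participants stopped after 8 mg count

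*Combined protocol and SAP*

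**What the plan says.** **Replacement.** Section 6.7.2: "If participants are withdrawn or discontinued early, enrollment will continue to meet a goal of 35 participants". The sentence makes no distinction between withdrawal before and after dosing, or between reasons.

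**Withdrawal after the first dose.** Under the index visit in 7.4.2, for a qualifying adverse event after the first dose, "the second dose will not be given and the participant will be withdrawn from the study without receiving subsequent doses". Section 2.1.4 says the same, and 6.7.1 lists such an event as a ground for termination. Section 6.7.1 adds that a reaction to the initial 8 mg is attributed to the standard dose, because only the later 24 mg is under evaluation.

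**Denominator.** Section 3.1 estimates the proportion among enrolled participants who receive 32 mg. Section 5.1.1 takes it among all study participants.

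**Sample size.** Section 6.4: "A total of 35 participants will be enrolled in the study with the goal of having 30 participants complete the study in its entirety". Section 6.6: "Recruitment will end when approximately 35 participants are enrolled". Section 10.1 gives no power calculation; the size rests on feasibility.

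**The concern.** The primary result is a single proportion from one open-label arm, and the stated hypothesis is that everyone who receives 32 mg will succeed. A few participants moved in or out of the denominator decide whether that hypothesis appears confirmed.

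A participant stopped at 8 mg fails the endpoint under the wording of both 3.1 and 5.1.1. The 3.1 denominator nevertheless removes that person, because it conditions on having received the full dose. Success in 3.1 requires receiving 32 mg, so under that denominator the completion part of the endpoint cannot fail. Section 6.7.2 then allows a new participant to be enrolled in the same place, so the final count of 35 shows no sign of the loss.

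The number of participants is also open. A team could stop at 35 enrolled or carry on until 35 remain, and could cite the protocol for either.

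**Working it through.** **1. The plan's own figure.** Section 6.4 gives 35 enrolled and 30 completing. The implied loss is 1 − 30/35 = 14.3%, and 30/(1 − 5/35) = 35. The two numbers agree if five losses are absorbed and none is replaced. There is no precision calculation to reproduce.

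**2. What the two counting rules imply for N.** With five early withdrawals, 6.4 and 6.6 stop at 35 enrolled. Section 6.7.2, read as replacement, runs to 35 + 5 = 40.

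**3. Effect on the primary proportion.** Assumptions, none of which the documents supply: k dosed participants are withdrawn after the first 8 mg; all others succeed; intervals are two-sided 95% exact (Clopper-Pearson).

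- 3.1 denominator with replacement: 35/35 for every k. The lower limit is 0.025^(1/35) = 90.0%, so the result is 100% (90.0 to 100).
- 3.1 denominator without replacement: (35 − k)/(35 − k).
- 5.1.1 denominator with replacement: 35/(35 + k).
- 5.1.1 denominator, 35 enrolled, no replacement: (35 − k)/35.

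| k | 3.1, not replaced | 5.1.1, replaced | 5.1.1, not replaced |
|---|---|---|---|
| 1 | 34/34 = 100% (89.7 to 100) | 35/36 = 97.2% (85.5 to 99.9) | 34/35 = 97.1% (85.1 to 99.9) |
| 2 | 33/33 = 100% (89.4 to 100) | 35/37 = 94.6% (81.8 to 99.3) | 33/35 = 94.3% (80.8 to 99.3) |
| 3 | 32/32 = 100% (89.1 to 100) | 35/38 = 92.1% (78.6 to 98.3) | 32/35 = 91.4% (76.9 to 98.2) |
| 4 | 31/31 = 100% (88.8 to 100) | 35/39 = 89.7% (75.8 to 97.1) | 31/35 = 88.6% (73.3 to 96.8) |

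The denominator is what moves the estimate. Replacement under 3.1 restores the sample to 35 and hides the loss. Replacement under 5.1.1 leaves the failures visible.

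**4. How large k might be.** The nearest figure in the documents is the chart review of 94 ED patients given 24 to 32 mg, with no adverse event observed (2.1.3, Safety). The exact upper 95% limit for 0/94 is 1 − 0.025^(1/94) = 3.8%, which is about 35 × 0.038 = 1.3 events in 35. That review describes patients who received the higher dose, so it says little about anyone stopped at a lower one.

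**The case against.** The strongest reply is that withdrawal is not deletion. Section 5.1.1 counts all study participants at the end of the index visit, and a dosed, withdrawn participant is still one of them. If 5.1.1 governs, replacement alone does not bias the estimate. This stands, but nothing says that 5.1.1 overrides 3.1.

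Setting first-dose reactions apart is also a disclosed choice (6.7.1). Adverse events are documented regardless of relationship (8.3) and tabulated (10.1), so reactions would still appear in the report. This too stands; what is affected is the primary proportion and its interval.

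A reader might infer more: that a reaction to BUP could be relabelled a screening failure, since 6.4 says that people meeting any exclusion criterion "will be withdrawn from the study if already enrolled as post-enrollment screen fails", 6.7.1 includes criteria that arise later, and one criterion is "Has a known allergy to BUP". The documents do not support that chain. The screen-failure wording occurs only in 6.4, directly after the eligibility and pre-treatment assessments, which is a pre-dose setting. Reactions after 8 mg have their own route in 6.7.1 and 7.4.2, and 6.7.2 lists removal for an adverse event separately from meeting an exclusion criterion. What remains true is that no sentence states a cut-off.

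A reader might also infer that 6.4 and 6.7.2 cannot both be followed. That is too strong. The five losses in 6.4 are people who do not complete the whole study and may be follow-up losses. Section 6.6 says approximately 35, and 6.7.2 could mean only that enrolment goes on to 35 in total. Projecting about 41 enrolled would require replacement to 35 completers, which 6.7.2 does not say.

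**Conclusion.** The point holds as a counting defect. Followed as written, 6.7.2 and 7.4.2 together with the 3.1 denominator allow participants who were dosed and stopped after a reaction to leave the primary proportion and be replaced. The 5.1.1 denominator would keep them. The plan does not say which applies, or what 35 counts.

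With 2 to 4 such participants and all others successful, the report would read 100% (90.0 to 100) instead of 94.6% (81.8 to 99.3) to 89.7% (75.8 to 97.1). The lower limit is then overstated by 90.0 − 81.8 = 8.2 to 90.0 − 75.8 = 14.2 percentage points. With one participant the overstatement is 90.0 − 85.5 = 4.5 points; with none it is zero. The counts and the interval method are assumptions.

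The explicit route concerns reactions after the first 8 mg. A listed clinically significant event related to the second dose already counts as failure under 5.1.1.

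**What to change.** Put one counting rule into 3.1, 5.1.1, 6.4, 6.7.1 and 6.7.2:

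- Post-enrolment screen failure and replacement apply only to an enrolled participant whose exclusion criterion is identified before any BUP is given after enrolment. Section 6.9.4 allows up to 8 mg to be given clinically before enrolment. For those participants the rule covers only criteria that were present at enrolment and are not a reaction to BUP. Without this clause, the same reaction would be counted differently according to who gave the first dose.
- Every other enrolled participant who has received BUP counts toward the 35, is not replaced, and stays in the 5.1.1 denominator. If 32 mg is not completed, the participant is counted as not successfully induced.
- Report pre-dose screen failures separately. Show first-dose reactions on their own line, so that they can be told apart from reactions to the 24 mg dose.

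The text should also say how it counts enrolled participants who never receive BUP for a reason other than an exclusion criterion, since 6.1 allows enrolment before the COWS threshold is reached. The rule above does not decide that case.

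The cost is wording in five sections, a possibly lower reported success rate, and somewhat fewer than 35 participants receiving the full dose if some are stopped early. No extra patients are needed, and withdrawal from dosing and clinical care are unchanged.
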